#### 8.2.3.4 Clinical outcomes

- **All-cause mortality at 30 days** will be
  - estimated by arm using the Kaplan-Meier method
  - compared between arms through pairwise comparisons using a log-rank test stratified by centre (three pairwise tests will be performed)
  - and the complementary log-log transformation will be applied to calculate the 95% confidence intervals for the 30-day survival estimates
- **All-cause mortality at 30 days** will be described only
- **In-hospital mortality**
  - will be described by arm as count and percentages
  - will be compared between arms using a logistic regression model adjusted on centre. Odds ratio will be reported with 95% confidence intervals
- Number of patients hospitalised after emergency and number of patients discharged after emergency will be described by arm as count and percentages
- **Length of hospital stay**
  - Will be analysed **among all randomized patients, and repeated among hospitalized patients only** (excluding those discharged after emergency department presentation)
  - Will be compared between arms using a linear regression model adjusted on centre with a bootstrap method for 95%CI.
  - Pvalues will be computed by inverting the corresponding confidence interval (Thulin 2024: modern statistics with R).
- **Unplanned transfer to the ICU/IMCU within 30 days after initial admission/evaluation**
  - Will be analysed **among all randomized patients, and repeated among hospitalized patients only** (excluding those discharged after emergency department presentation)
  - Will be described by arm as count and percentages
  - Will be compared between arms using a logistic regression model adjusted on centre. Odds ratio will be reported with 95% confidence intervals.
- The following outcomes will be described by arm as count and percentages **in patients discharge alive**. Those outcomes will not be compared between arms:
  - **Admission to rehabilitation through 3 months in patients discharge alive**
  - **Transfer to LTCF through 3 months in patients discharge alive**
  - **All-cause readmission to acute care setting in patients discharge alive**
  -
- The **quality of life 30 days and 90 days** will be described by arm as median and IQR **in patients discharge alive**. Quality of life will not be compared between arms

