3. STUDY OBJECTIVES AND DESIGN

3.1 Hypothesis and primary objective

Overall aim: To compare the diagnostic, therapeutic and clinical outcomes of three diagnostic strategies based on CXR (standard care), low-dose CT scan (LDCT) or lung ultrasonography (LUS) in elderly patients with suspected community or nursing-home acquired pneumonia in the ED.

Primary objective: To evaluate whether a diagnostic strategy using LDCT compared with CXR leads to a more accurate diagnosis in suspected pneumonia.

Secondary objectives:

Diagnostic objectives:

- To assess the difference in diagnostic accuracy for patients with suspected pneumonia using LUS compared to CXR, and using LUS compared to LDCT
- To assess sensitivity and specificity of CXR, LDCT and LUS; the number of additional imaging studies and invasive procedures prescribed during the acute setting; the imaging studies needing unmasking in emergency; the incidentalomas.

Treatment objectives: to assess whether there is a difference between the diagnostic strategies in:

- Antibiotic consumption up to one month

Clinical objectives: to assess whether there is a difference between the diagnostic strategies in:

- Time to clinical stability
- Length of hospital stay

- Unplanned transfer to the intensive care unit or operating room
- Admission to rehabilitation/long-term care facility (LTCF) up to 3 months
- All-cause mortality up to 3 months
- All-cause readmission up to 3 months
- Quality of life at admission, discharge and 3 months

Cost outcomes

Diagnosis concordance between physicians at the ER and experts

The association of biomarkers and the presence of an infiltrate.

GEROBIOTA objectives

To identify factors associated with the probability of pneumonia, and aspiration pneumonia, 1 month and 1 year mortality, 1 year readmission and to create a biobank allowing the assessment of inflammation, immune status and genetic markers.

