#### Clinical outcomes

- Time to clinical stability
- Hospital admission
- Length of hospital-stay
- ICU admission
- Transfer to rehabilitation or long-term care facility (LTCF)
- All-cause ICU readmission
- In-hospital mortality
- All-cause mortality at 30 days and at 90 days
- Quality of life at 30 days and at 90 days

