### 3.4 Timing of outcome assessments (timepoints)

Study periods	Timeline of patient enrolment/allocation, interventions and assessments						
	Screening	Randomisation	Discharge from ER	Discharge from the acute setting	Day 30	Day 90	Reference diagnosis
Visit	1	2	3	4	5	6	7
Time (hour, day)	hr0	hr2*	hr6*	dx	d30	d90	
Demographics	x						
Medical history	x						
Inclusion/exclusion criteria	x						
Physical examination	x						
Vital signs	x						
Laboratory tests	x			x			
CXR, LDCT, LUS		x					
Main diagnosis before ER discharge			x				x
Other diagnosis outcomes		x		x			x
Number of antibiotic free days					x		
Clinical, safety and cost outcomes			x		x		
Readmission and mortality					x	x	
QoL questionnaire			x		x	x	
Panel of experts							x

\*Approximately.  
CXR, chest x-ray; d, day; ER, emergency room; hr, hour; LDCT, low-dose CT; LUS, lung ultrasonography; QoL, quality of life.

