- **All-cause mortality within 30 days** will be defined as a death date (*death\_date* or *deathdate*) occurring within **30 days** of the emergency entry date (*emergencydate*)

- **All-cause mortality within 90 days** will be defined as a death date (*death\_date* or *deathdate*) occurring within **90 days** of the emergency entry date (*emergencydate*)

- **In-hospital mortality** will be defined as a death occurring on or before the hospital discharge date (*hospital\_discharge\_date*), based on the recorded death date (*death\_date* or *deathdate*)

- **All-cause readmission within 90 days** after initial emergency admission/evaluation will be defined as a readmission date (*readmission\_date*) occurring within **90 days** of the emergency entry date (*emergencydate*)

- **Quality-of-life at 30 days and 90 days** (*eq5d\_score*)

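### SAP 8.2.3.4 gives two conflicting rules for 30-day mortality and none for 90 days; Section 9 declares neither the loss of the protocol's 3-month comparison nor at least nine other departures

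*SAP*

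**What the plan says.** SAP 8.2.3.4 has two entries with the same label, all-cause mortality at 30 days. The first asks for Kaplan-Meier estimates by arm, which are to be "compared between arms through pairwise comparisons using a log-rank test stratified by centre (three pairwise tests will be performed", and adds that "the complementary log-log transformation will be applied to calculate the 95% confidence intervals for the 30-day survival estimates". The second says that the outcome "will be described only". No mortality entry in that section names 90 days.

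The longer horizon is present elsewhere in the SAP. Section 3.3.2 lists "All-cause mortality at 30 days and at 90 days". Section 8.1.2.4 defines "All-cause mortality within 90 days" as a separate outcome. The schedule in 3.4 marks "Readmission and mortality" at both day 30 and day 90.

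Protocol 3.1 includes "All-cause mortality up to 3 months" among the outcomes on which the strategies are to be compared. Protocol 5.1, secondary analysis 8, plans Kaplan-Meier curves and a log-rank test stratified by site over the 3-month follow-up.

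SAP Section 9 is the record of departures from the protocol. It declares in-hospital mortality and two subgroups (chronic pulmonary disease, obesity) as additions. It declares one analysis as not conducted: time to clinical stability.

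**The concern.** An analyst cannot follow both entries for 30-day mortality, and has no instruction for 90-day mortality. More important, a stated protocol objective has lost its between-arm comparison without any declaration.

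Section 1 of the SAP says that it was finalised after enrolment and before analysis. With a plan of that date, readers rely on the departures section to tell a reasoned change from an oversight. If the section is incomplete, they cannot do so. The omissions include the primary test itself and two robustness checks on the primary outcome.

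**Working it through.** There is no figure to reproduce. The check sets the texts side by side.

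**Mortality.** The first entry cannot be the misprinted one, because its last line refers explicitly to 30-day estimates. Section 8.1.2.4 defines the 30-day and 90-day outcomes in that order, so the second entry was probably meant for 90 days. That leaves two readings:

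- Literal: 30-day mortality has two incompatible rules and 90-day mortality has none.
- Slip: 30-day mortality is tested and 90-day mortality is only described.

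Neither reading contains a comparison to day 90. The between-arm test of in-hospital mortality, also in 8.2.3.4, stops at discharge and does not replace it.

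**Other departures.** None of the following appears in SAP Section 9.

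| Item | Protocol | SAP |
|---|---|---|
| Primary test | 5.1: logistic regression adjusted for site | 8.2.2.1: Cochran-Mantel-Haenszel risk difference stratified on centre |
| Antibiotic outcome | 5.1, item 6: non-parametric competing-risk analysis | 8.2.3.3: linear regression on antibiotic-free days, bootstrap interval |
| Length of stay | 5.1, item 8: Mann-Whitney | 8.2.3.4: linear regression, bootstrap interval |
| Readmission | 5.1, item 8: survival models with death as competing event | 8.2.3.4: counts only, for "All-cause readmission to acute care setting in patients discharge alive" |
| Imaging order | 5.1: sensitivity analysis leaving out patients whose CXR preceded LDCT and LUS | Absent from 8.2.2.5 and 8.2.2.6 |
| Missing outcome data | 5.2: complete case, plus multiple imputation above 10% missing | 8.4: complete case only |
| Sensitivity, LUS v LDCT | 5.1, item 3: compared | 8.2.2.3: CXR v LDCT and CXR v LUS only |
| Viral subgroup | 5.1: any virus on PCR | 8.2.2.6: SARS-CoV-2 only |
| Aspiration subgroup | Not planned | 8.2.2.6: added |

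That is nine departures besides mortality, or ten in all. The list is not claimed to be complete. Cost, biomarker and ancillary analyses are not counted, because SAP Section 1 assigns them to a separate plan.

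Incidentalomas belong in a different class. Protocol 3.2 lists their prevalence as an outcome and the SAP omits it, but Protocol 5.1 gives no analysis for them. They are an omitted outcome, not a dropped analysis.

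**The case against.** *It is a one-word slip.* Probably so, but correcting the word leaves 90-day mortality described and not compared, and still undeclared.

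*The SAP complements the protocol, so anything it omits still stands.* SAP Section 1 does say that it complements the protocol. It also says that it sets out all the statistical methods to be used and covers only the analyses it describes. A reader cannot tell which statement governs an omitted analysis.

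*A SAP written before analysis may change secondary analyses.* This stands. Several changes may be sensible: the antibiotic analysis now matches the outcome named in Protocol 3.2 (antibiotic-free days at day 30), and the new primary method still respects stratification by centre. For most items, declaring the change with a reason would be enough. The day-90 mortality test is different because it serves a stated objective and uses data already scheduled.

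*Restoring it adds overlapping tests.* This also stands. Three pairwise tests at day 30 plus three at day 90 make six, all at the unadjusted 0.05 of SAP 4.1, besides in-hospital mortality. The fix must say which is the protocol's comparison.

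Two stronger readings are tempting. A reader might treat days 31 to 90 as a measure of the information lost. The documents give no mortality rate and no timing of deaths, so the calendar interval says nothing about the share of events left uncompared. A reader might also infer from the planned 10% drop-out that the imputation rule was likely to apply. Drop-out is not the same as a missing primary outcome here: the clinician's rating is made before the patient leaves the ED (Protocol 4.3 and 5.2), and the panel adjudicates all patients. SAP 8.4 expects little missing data, and complete case was already the protocol's primary approach.

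**Conclusion.** The point holds. As printed, 8.2.3.4 contradicts itself on 30-day mortality and is silent on 90-day mortality. On either reading the protocol's 3-month comparison between arms is gone and Section 9 does not declare it. A description at 90 days might still include survival curves; what is certainly lost is the test.

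Section 9 names one dropped analysis, while at least ten departures, counting mortality, go undeclared. This should be corrected, but it does not invalidate the trial. The mortality defect leaves the primary endpoint and the sample size untouched. A reader should not take that to mean that the primary method is unchanged, since its test is among the undeclared changes. Nor do the documents show that any of these changes biases a result: the finding concerns specification and transparency. It rests on the text alone and needs no assumption about event rates.

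**What to change.** Before database lock:

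- Correct the second mortality entry to 90 days, and apply the protocol's Kaplan-Meier estimates by arm and centre-stratified log-rank test to day 90.
- Keep the 30-day analysis, because Protocol 3.2 names 1-month mortality as a safety outcome. State that the 3-month comparison is the protocol's mortality comparison, so that the overlapping unadjusted tests are not read as equal.
- Restore the imputation rule above 10% missing for the primary outcome. Restore the imaging-order sensitivity analysis if the order was recorded, which the cited sections do not confirm. Otherwise declare the removal of each.
- For every other item in the table, restore the protocol's analysis or list the change in Section 9 with a reason. Record incidentalomas there as an omitted outcome, or report them.

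The cost is one corrected entry, a fuller Section 9, a few standard analyses and one more set of unadjusted secondary tests. Mortality and readmission are already scheduled at day 30 and day 90, so no new patients or visits are needed.

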Safety outcomes: unplanned transfer to the ICU; 1-month mortality.

[figure not shown]
GEROBIOTA:

The probability of pneumonia/aspiration pneumonia according to the panel of experts, all cause 1 month and 1 year mortality, 1 year readmission for pneumonia.

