4.4 Withdrawal and discontinuation

Withdrawal:

If a patient wishes to withdraw consent, the investigator will be informed, and the patient will be excluded from the study without any consequence on his care.

As the validity of the clinical trial or its results could be distorted in essential points by the destruction of biological material and personal health-related data, their use in the clinical trial will be allowed despite the refusal of the patient. Since pneumonia is very frequent in elderly patients and since this population is very rarely included in clinical trials, we think it is very important to carry out this trial and not to destroy data which would be valuable for further elderly patients having pneumonia.

In case of protocol violation, the patient will stay in the randomized arm for the intention to treat analysis and will be excluded from the arm for the per protocol analysis. If the patient gets lost to follow-up, the data will be censored after the last visit. In case of death, the civil registry will be consulted regarding the information on mortality.

Death of the patient:

In case of death before obtaining provisional consent, there will be no inclusion.

In case of death of the person after provisional consent, it will be verified whether the patient has issued Advance Directives authorizing the use of data or biological materials for research purposes. If this is not the case, the consent of the representative will be necessary.

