#### 8.1.2.4 Clinical outcomes

- **Number of days requiring oxygen therapy** will be analysed for descriptive purposes only.
- **Length of stay (in the acute care setting)** will be calculated as the number of days between the emergency entry date (*emergencydate*) and the hospital discharge date (*hospital\_discharge\_date*)
  - A stay of 1 day corresponds to admission and discharge on the same calendar day.
  - A stay of 2 days corresponds to discharge on the day after admission, and so on.
- **Discharge after emergency** will be defined as a hospital stay of 1 day – that is, when the emergency entry date (*emergencydate*) and the hospital discharge date (*hospital\_discharge\_date*) fall on the same calendar day.
- **Transfer to the ICU/IMCU within 30 days** after the initial emergency admission/evaluation will be considered as having occurred if **either** of the following conditions is met:
  - The time between emergency entry date (*emergencydate*) and the hospital discharge date is  $\leq 30$  days **and** the discharge destination (*discharge\_place*) is ICU or IMCU; or
  - The 1-month follow-up visit reports a transfer to ICU (*transfer\_to\_icu*) or IMCU (*transfer\_imcu*), **and** the delay between the emergency entry date (*emergencydate*) and the ICU/IMCU admission date (*icu\_transfer\_date* or *imcu\_transfer\_date*) is  $\leq 30$  days
- **Transfer to a rehabilitation unit within 90 days** after the initial emergency admission/evaluation will be considered as having occurred if **either** of the following conditions is met:
  - The discharge destination (*discharge\_place*) is rehabilitation and the delay between *emergencydate* and *hospital\_discharge\_date* is  $\leq 90$  days; or
  - A transfer to rehabilitation (*rehabilitation*) with a corresponding admission date (*rehabilitation\_date*)  $\leq 90$  days after *emergencydate* is reported at the 1- or 3-month follow-up.
- **Transfer to a long-term care facility (LTCF) within 90 days** after the initial emergency admission/evaluation will be considered as having occurred if **either** of the following conditions is met:

- The discharge destination (*discharge\_place*) is LTCF and the delay between *emergencydate* and *hospital\_discharge\_date* is  $\leq$  90 days; or
- A transfer to LTCF (*transfer\_ltcf*) with a corresponding admission date (*ltcf\_transfert\_date*)  $\leq$  90 days after *emergencydate* is reported at the 1- or 3-month follow-up.

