**Note: If an event is reported at multiple follow-up visits, the earliest available date will be used for analysis.**

## 8.2 Analysis methods

If not otherwise stated, the analyses will be performed on the full analysis set.

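### In the ICU/IMCU comparison a death without transfer is coded as no event, so that odds ratio read alone can understate harm; the analysis sets for the safety outcomes also conflict

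*SAP*

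**What the plan says.** Protocol 3.2 names two safety outcomes together: "Safety outcomes: unplanned transfer to the ICU; 1-month mortality".

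SAP 8.1.2.4 makes ICU/IMCU transfer a yes/no variable. A transfer within 30 days "after the initial emergency admission/evaluation will be considered as having occurred if" either of two conditions is met. The first is a discharge destination of ICU or IMCU within 30 days of emergency entry. The second begins "The 1-month follow-up visit reports a transfer to ICU" (or IMCU) and requires a transfer date within 30 days. Death appears in neither condition.

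SAP 8.2.3.4 lists the outcome as "Unplanned transfer to the ICU/IMCU within 30 days after initial admission/evaluation" and says that it "will be compared between arms using a logistic regression model adjusted on centre. Odds ratio will be reported with 95% confidence intervals", the same wording that it uses for in-hospital mortality. No competing event or composite is named. Protocol 5.1 (secondary analysis 8) also plans site-adjusted logistic regression for ICU transfer, so the SAP follows the protocol here.

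Three analysis sets are in play:

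- ICU transfer is analysed "among all randomized patients, and repeated among hospitalized patients only" (SAP 8.2.3.4).
- Mortality has no stated set, so the default in SAP 8.2 applies: "If not otherwise stated, the analyses will be performed on the full analysis set". SAP 4.2.1 removes from that set eligibility violations, patients who had none of the exams, and patients with no data after randomisation.
- SAP 4.2.3 assigns all safety-related analyses to a safety set, grouped by the imaging method actually received.

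SAP 8.2.3.4 also carries two bullets under the label of 30-day all-cause mortality. One compares arms by stratified log-rank test. The other says that the outcome is only described.

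**The concern.** A patient who dies on the ward on day 3 without a transfer and a patient who recovers without incident get the same code in the ICU model. If one arm has more early deaths, fewer of its patients can go on to be transferred. If deaths occur in place of transfers, the arm can show fewer ICU events because it does worse. Such deaths are plausible here: the protocol's earlier cohort had a median age of 84, and only patients whose care plan is limited to comfort care are excluded.

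This matters because ICU transfer is one of the two safety outcomes that the protocol names. A reader who takes its odds ratio as a safety statement could draw the wrong conclusion about an imaging strategy. It would also be hard to set the ICU and mortality results side by side if they came from different sets of patients.

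**Working it through.** **Plan's own figure.** The documents state no rate, event count or power for ICU transfer or death, so there is nothing to reproduce. Every rate below is an assumption, chosen to show direction and range. Arm B is the arm with more deaths. For two risks, the odds ratio (OR) is [pB/(1−pB)] / [pA/(1−pA)].

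**Case 1: deaths only remove time at risk.** The ICU hazard is the same in both arms and constant over 30 days. Let r_I be the 30-day ICU risk without deaths, and r_D the 30-day risk of death without ICU if nobody were transferred.

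- h_I = −ln(1−r_I)/30 and h_D = −ln(1−r_D)/30
- ICU proportion = h_I/(h_I+h_D) × [1 − exp(−30(h_I+h_D))]
- Death-or-ICU proportion = 1 − (1−r_I)(1−r_D)

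Example with r_I = 10% and r_D = 5% in A, 20% in B. The ICU proportion is 0.0975 in A and 0.0898 in B, so the OR is 0.91. Death-or-ICU is 0.145 in A and 0.280 in B, so the OR is (0.280/0.720)/(0.145/0.855) = 2.29.

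| r_I | r_D, A v B | ICU OR, B v A | Death-or-ICU OR |
|---|---|---|---|
| 10% | 5% v 10% | 0.97 | 1.38 |
| 10% | 5% v 15% | 0.94 | 1.81 |
| 10% | 5% v 20% | 0.91 | 2.29 |
| 5% | 5% v 10% | 0.97 | 1.57 |
| 5% | 5% v 15% | 0.95 | 2.21 |
| 5% | 5% v 20% | 0.92 | 2.92 |

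The ICU line hardly moves, but it shows nothing of the extra deaths.

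**Case 2: deaths replace transfers.** The inputs are observed proportions, ICU + death without ICU.

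| Arm A | Arm B | ICU OR | Death-without-ICU OR | Death-or-ICU OR |
|---|---|---|---|---|
| 10% + 5% | 5% + 10% | (0.05/0.95)/(0.10/0.90) = 0.47 | 2.11 | 1.00 |
| 8% + 5% | 5% + 10% | (0.05/0.95)/(0.08/0.92) = 0.61 | 2.11 | (0.15/0.85)/(0.13/0.87) = 1.18 |
| 10% + 5% | 7% + 8% | (0.07/0.93)/(0.10/0.90) = 0.68 | 1.65 | 1.00 |

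Here the ICU line favours the arm with more deaths, while death-or-ICU is equal or worse in that arm.

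**Precision at the planned 165 per arm.** SE of the log OR with e events in each arm = √[2(1/e + 1/(165−e))].

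- 8 events per arm: SE 0.513, so the 95% interval extends by a factor of exp(1.96 × 0.513) = 2.73 each way.
- 23 events per arm: SE 0.318, factor 1.86.

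**Limit of the composite.** Take A 7% + 8% and B 4% + 13%. The ICU OR is (0.04/0.96)/(0.07/0.93) = 0.55. The OR for death without ICU is (0.13/0.87)/(0.08/0.92) = 1.72. The composite OR is (0.17/0.83)/(0.15/0.85) = 1.16, with a 95% interval of about 0.64 to 2.1 at 165 per arm. The composite removes the false reassurance but dilutes an effect confined to death.

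**Analysis sets.** SAP 3.1 and 3.8 state that all three exams were performed for each patient. Grouping by imaging received would therefore place nearly every patient in all three groups, so the set in SAP 4.2.3 cannot define a comparison between arms. The gap between all randomised patients and the full analysis set cannot be sized, because the documents do not say how many patients the latter excludes.

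**The case against.** The strongest reply has three parts.

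**Deaths are already compared.** SAP 8.2.3.4 compares 30-day mortality by stratified log-rank and in-hospital mortality by logistic regression. A ward death without transfer counts in the first, and in the second as well if it falls on or before hospital discharge. Protocol 7.1 has the safety board weigh both ICU transfer and mortality. This stands: a reader might infer that the plan hides harm overall, and it does not. The safeguard is weakened only by the two contradictory 30-day bullets. One may have been meant for 90-day mortality, which SAP 8.1.2.4 defines and SAP 8.2.3.4 otherwise omits, but that is an inference.

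**The coding is a legitimate estimand.** When status is known to day 30 or death, the proportion transferred with deaths as non-events is the cumulative incidence of ICU transfer with death as a competing event. A competing-risk estimate would give the same percentage. This also stands, which is why the remedy is a supplementary composite and not a different ICU model.

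**Missing 1-month data are not scored as no event.** A reader might infer that they are, or that a patient who went to ICU, came back and then died cannot be counted. The documents support neither. SAP 8.4 prescribes complete-case analysis. SAP 8.1.2.3 computes antibiotic-free days for deceased patients from first-month data, and SAP 8.1.2.2 records a procedure from the acute stay in the 1-month instrument. That form therefore appears to cover in-hospital events and patients who died. The coding of an absent form is simply not spelled out. Protocol 4.4 says in general terms "If the patient gets lost to follow-up, the data will be censored after the last visit", which does not settle a yes/no variable. If missing forms were scored as no event, with 10% true ICU risk and 5%, 10% or 20% missing in one arm only, the OR would be 0.95, 0.89 or 0.78. Under complete case with data missing at random it is 1.00.

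On the sets, the phrase about all randomised patients may mean only that patients discharged from the emergency department are kept. The conflict does not itself make an arm look safer. It still leaves the analyst without a clear instruction.

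**Conclusion.** The point holds for the ICU line. Death without transfer is coded as no event, and the resulting odds ratio can understate harm or look favourable in an arm with more early deaths. On assumed rates the ICU odds ratio is about 0.91 to 0.97 if deaths only remove time at risk. It is about 0.47 to 0.61 if deaths replace transfers, or 0.68 in the mildest split tried. Which case applies is unknown, because the documents give no rates.

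The three analysis sets conflict on the plain text, and the one grouped by imaging received cannot separate arms. The size of that problem is unknown, and it is a separate matter from the effect of deaths. Neither matter touches the primary outcome. Both should be settled before database lock.

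**What to change.** 1. Report death or ICU/IMCU transfer within 30 days, with the same centre-adjusted logistic model, as a supplementary safety comparison beside the ICU-only and mortality results. Always show the components.
2. Analyse ICU transfer, 30-day mortality and the composite in one set: all randomised patients, by allocated arm. Reconcile SAP 4.2.3, 8.2 and 8.2.3.4 accordingly.
3. As clarification only: state that ICU status is no only when it is known to day 30 or to death, and is otherwise missing. Reconcile the two 30-day mortality bullets in SAP 8.2.3.4.

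The cost is SAP wording and one variable derived from the transfer and death dates that SAP 8.1.2.4 already lists. The downside is one extra reported comparison, and a composite that can dilute an effect confined to death.
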